8.4. Interim Analysis

During Part 1, following completion of the Active Period by all Cohorts, the database will be cleaned and locked.

During Part 2, an interim analysis will occur at 18* confirmed cases of SARS-CoV2 infection. In addition to efficacy, this interim analysis would also include evaluation of safety and immunogenicity through Week 8. If 18 confirmed cases are not identified, the study will be considered complete at 6 months post last vaccination and the database will be locked and unblinded. At this time the efficacy analysis will be conducted, O'Brien-Fleming methods will be used for halting rules (O'Brien, 1979):

- If P = 0.003 at the interim analysis, the study may be stopped for overwhelming efficacy.
- If the study completes as planned (i.e., 6 months post last vaccination), it will be determined to be successful if $P \le 0.05$.

*VE null = 30% (since that is lower bound from the FDA) and VE_Alt = 80% and ARU = 0.05 we get p0 = 0.41 and p1 = 0.17 which gives a total target number of events of around 31 (with ~5 from vaccine group and 26 in placebo so if we add in the other dose then looking at around 36 total events) using POT0 if we simplify down to one primary dose vs placebo calculation. So interim analysis at 1/2 * 36 = 18 events (or 6 months post last vaccination, whichever is first) (Follmann, 2020).

The SAP will describe the planned interim analysis in greater detail.

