8. STATISTICAL CONSIDERATIONS

8.1. Sample Size Determination

8.1.1. Part 1

Part 1 is an open-label, lead in, repeat-dose, dose and age escalation design to evaluate the VXA-COV2-1.1-S oral vaccine in two cohorts with repeat dose administration. Cohort 1 will enroll approximately a total of 36 healthy adult participants that are naive (no prior vaccination against SARS-CoV-2 infection and no history of prior COVID-19 or SARS-CoV-2 infection) across 3 groups of 12 subjects each, encompassing 2 age groups and two dose levels. Cohort 2 will enroll approximately a total of 36 healthy adult participants who have received two doses of an EUA or FDA approved mRNA vaccine for the prevention of SARS-CoV-2 infection across 3 groups of 12 subjects each, encompassing 2 age groups and two dose levels.

There are no sample size calculations utilized for Part 1; the cohort size is estimated to provide informative safety and immunogenicity data to allow dose selection for safely proceeding to Part 2.

8.1.2. Part 2

The number of participants to be randomized in Part 2 (VXA-CoV2-1.1-S and placebo) is predicted to yield meaningful immunogenicity and efficacy results to inform how best to proceed into later stage studies. In previous human studies with Ad5 vectored oral tableted vaccines using the same vaccine platform (Ad5 vectored vaccine coding for target virus-specific antigens and a dsDNA adjuvant), the vaccine was well tolerated at total doses up to $2x10^{11}$ IU.

All testing will be performed at alpha = 0.05. All tests will be two-sided. Assuming attack rate in unvaccinated group (ARU) = 5% and vaccine efficacy (VE) = 90%, 341 participants would be required per treatment arm, yielding 95% power.

The total sample size for Part 2 of this study (2 arms) would be 682. To allow for a $\sim 15\%$ dropout rate, 800 participants will be randomized.

2-sided Alpha	0.05	0.05	0.05	0.05	0.05	0.05	0.05	0.05
ARU	5%	5%	5%	5%	5%	5%	5%	5%
VE	90%	90%	90%	90%	95%	95%	95%	95%
Power	80%	85%	90%	95%	80%	85%	90%	95%
SS/Arm	207	236	276	341	177	202	236	292
Sample Size (part 2 of								
study, two arms)	414		472	682	354	404	472	584

Unvaccinated Atta	ck Rate (ARU): 5%
--------------------------	-------------------

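### The Section 8.4 event target of about 31 (raised to 36) does not fit 800 participants at a 5% attack rate, which yield about 20.5 to 24 cases at VE 80%, so the 18-case interim is not a half-way look

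*Combined protocol and SAP*

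**What the plan says.** The asterisk on the 18-case trigger in protocol Section 8.4 leads to a footnote with these inputs: "VE null = 30% (since that is lower bound from the FDA) and VE_Alt = 80% and ARU = 0.05". From them, "we get p0 = 0.41 and p1 = 0.17 which gives a total target number of events of around 31". The footnote splits the target and then enlarges it: "with ~5 from vaccine group and 26 in placebo so if we add in the other dose then looking at around 36 total events". The trigger follows: "So interim analysis at 1/2 * 36 = 18 events (or 6 months post last vaccination, whichever is first".

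Section 8.1.2 sizes Part 2 separately: "Assuming attack rate in unvaccinated group (ARU) = 5% and vaccine efficacy (VE) = 90%, 341 participants would be required per treatment arm", for 95% power. After allowing for about 15% dropout, "800 participants will be randomized". Table 2 and Section 4.2.1 give two arms, one active dose and placebo, 400 each.

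The calendar sets the end of data collection. Section 4.2.2 runs the efficacy period to the last participant's Month 7 visit, and Section 8.4 says "If 18 confirmed cases are not identified, the study will be considered complete at 6 months post last vaccination". Final success is P of 0.05 or less, with no null VE named. No rule ties the final analysis to 31 or 36 cases.

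**The concern.** Sections 8.1.2 and 8.4 use the same 5% attack rate, but the footnote's 26 placebo cases are more than 400 placebo participants would produce at that rate. The total matters because the interim trigger is defined as a fraction of it. If the trial is expected to finish well short of 36, a look at 18 cases comes late, and a boundary tied to a half-way look no longer matches the information available. The footnote is also the only place where the protocol discusses a 30% lower bound. A reader could take 31 as the case count supporting a conclusion that VE exceeds 30%, and could later read a failure to show it as a weak vaccine when too few cases were the cause.

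**Working it through.** **Inputs.** From Section 8.4: null VE 30%, alternative VE 80%, attack rate 5%, target 31 raised to 36, interim 18. From Section 8.1.2: 341 per arm, VE 90%, two-sided alpha 0.05, 800 randomized. From Table 2: 400 per arm, 1:1.

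**1. Reproduce the plan's figures.** With 1:1 allocation, the chance that a case falls in the vaccine arm is (1 − VE)/(2 − VE).
- p0 = 0.7/1.7 = 0.412 and p1 = 0.2/1.2 = 0.167, which match 0.41 and 0.17. Both depend on VE alone; the attack rate does not enter.
- Section 8.4 states no power for the 31. An exact binomial test at one-sided 0.025 with 31 cases rejects at 7 or fewer vaccine cases (actual alpha 0.0245) and has 86.8% power at VE 80%. Thirty-one is the smallest count with at least 85% power, so 85% is an assumption that reproduces it.
- Split: 31/6 = 5.2 vaccine and 25.8 placebo, as stated. The 36 is 26 + 5 + 5, that is, two dose arms and placebo.
- The 341 per arm in Section 8.1.2 reproduces as a two-proportion comparison of 5% with 0.5%, a test against VE = 0.

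**2. Expected cases** = n per arm × 0.05 × (2 − VE).

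| n per arm | VE 80%: placebo + vaccine | VE 80% total | VE 90% total |
|---|---|---|---|
| 341 | 17.05 + 3.41 | 20.5 | 18.8 |
| 400 | 20 + 4 | 24.0 | 22.0 |

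Against 31, the VE 80% totals are short by 23% (1 − 24/31) to 34% (1 − 20.46/31). The Poisson probability of 31 or more cases is 0.018 at 20.5 and 0.096 at 24.

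**3. What 31 would need.** At 5% and VE 80%: 31/(0.05 × 1.2) = 517 per arm. With the planned numbers, the attack rate would have to be 31/(400 × 1.2) = 6.5% or 31/(341 × 1.2) = 7.6%.

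**4. Where 18 cases falls.** The plan intends 18/36 = 50%. At VE 80%, 18/24 = 75% and 18/20.46 = 88%. At VE 90%, 18/22 = 82% and 18/18.755 = 96%.

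**5. Power if the final null is VE = 30%** (exact conditional test, one-sided 0.025, averaged over independent binomial case counts in each arm).

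| Design | VE 80% | VE 90% |
|---|---|---|
| 341 per arm, 5% | 58% | 84% |
| 400 per arm, 5% | 67% | 91% |
| Expecting 31 cases at VE 80% (517 per arm, 5%) | 81% | – |

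On the same averaging, the loss at VE 80% is 14 to 24 points. The 86.8% in step 1 is for exactly 31 cases, a high point of a discrete test (30 cases give 78%), so it is not the right comparator for averaged power.

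**6. Power if the final null is VE = 0.** By the same method at VE 80%, power is 85% (341 per arm) to 91% (400 per arm).

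**The case against.** The best defence is that the footnote only explains the interim trigger. Section 8.4 attaches no power to 31 and does not require 31 or 36 cases at the end. The trial is sized in Section 8.1.2 against VE = 0, and that calculation is sound. Section 8.1.2 also describes the aim as informing later-stage studies. This stands as a limit on the consequence: a reader might infer that Part 2 is underpowered for its primary test, but the documents never assign VE = 30% to that test, and against VE = 0 power at VE 80% is 85% to 91%.

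A second defence is that follow-up may exceed six months. No time period is attached to the 5%, and early enrollees stay in the efficacy period until the last participant's Month 7 visit, although Section 4.2.4 puts efficacy evaluation at about six months. Participants who drop out can also contribute person-time first, so 20.5 is a floor. This stands too. A reader might infer that 31 cases cannot be reached; the supportable statement is that they are not expected. Closing the gap takes 29% (31/24) to 52% (31/20.46) more cases than 5% gives, and the protocol nowhere says it relies on that.

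Neither defence rescues the trigger. Eighteen is defined as half of a total that includes an arm Part 2 lacks and exceeds what the stated enrolment and attack rate would produce.

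**Conclusion.** The point holds as an inconsistency within Section 8. At the footnote's own 5% and VE 80%, Part 2 is expected to yield about 20.5 to 24 cases by Month 7, against a target of 31 and an inflated 36. The planned half-way look would come at about 75% to 88% of expected final cases (82% to 96% at VE 90%). This assumes that the 5% covers the whole efficacy period.

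The effect on power is conditional. If the final null is VE = 30% at two-sided 0.05, average power at VE 80% is about 58% to 67% instead of about 81%; at VE 90% it is 84% to 91%. At one-sided 0.05 and VE 80% it would be 70% to 78%. The 95% power in Section 8.1.2, for VE 90% against VE = 0, is not affected.

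A reader might also infer that the 31 was built on a higher attack rate. It was not: p0 and p1 use VE only, and the 5% is listed but unused in that step. The 6.5% to 7.6% is what this enrolment would need to reach 31, not what the footnote assumed.

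**What to change.** In Section 8.4 and the SAP:

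1. Replace 31 and 36 with the projected Month 7 cases at a 5% attack rate and 341 to 400 per arm: about 20 to 24 at VE 80% and 19 to 22 at VE 90%. Alternatively, keep 31 and state that reaching it with this enrolment needs an attack rate of about 6.5% to 7.6%. In either case, drop the addition for a second dose arm and state the period the attack rate covers.
2. Restate the information fraction at 18 cases and re-derive the O'Brien-Fleming interim and final boundaries for it, or reset the trigger to half of the projected cases. Replacing 31 and 36 without this step would leave 18 with no derivation.
3. Name the null VE for the final P ≤ 0.05 test. If it is 30%, give the power for VE above 30%: about 58% to 67% at VE 80% and 84% to 91% at VE 90%.

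No change in enrolment is needed. The cost is protocol and SAP text plus a boundary recalculation, and the stated figures become less favourable. Section 8.4 already leaves interim detail to the SAP, which Section 8.3 says is finalized before database lock.

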4.2.1. Part 2: Enrollment and Initial Vaccination

On Day 1, eligible participants will be randomized in a 1:1 ratio to either active (VXA-CoV2-1.1-S) or control (matching placebo tablets) group. (Table 2):

- Active: VXA-CoV2-1.1-S (dose to be selected from Part 1)
- Control: matching placebo

During the Active Period, participants will record daily symptoms of reactogenicity for 1 week post each study drug administration (Day 1 and Week 4), using a Solicited Symptom Diary. Participants will return to the site at 1 and 4 weeks following each vaccination, as specified in the SoA to have safety assessments and samples collected for evaluation of immunogenicity (Table 4).

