Interim looks at the efficacy using O'Brien Fleming Boundaries. One interim analysis may be conducted during the study by the IDMC if 18 confirmed cases of COVID-19 are observed prior to the completion of Month 7 visits, 6 months following the second vaccination, by all subjects. Given a power estimate of 95%, the study may be stopped by the Sponsor for overwhelming efficacy at the interim look if alpha ≤ 0.003 . The study will continue if this criterion is not met (and may be continued even if it is met per Sponsor's review and FDA agreement). If the decision is made to continue the study until completion at 6 months post last vaccination, alpha ≤ 0.05 .

Analysis Population	Description
Screened	All subjects who enter screening (assigned a screening number)
Randomized	All participants who are assigned a randomization number
Dose 1 evaluable immunogenicity	All eligible randomized participants who receive the study intervention to which they are randomly assigned at the first dose, have at least 1 valid and determinate immunogenicity result after Dose 1, have blood collection within an appropriate window after Dose 1, and have no other important protocol deviations.
Dose 2 evaluable immunogenicity	All eligible randomized participants who receive 2 doses of the study intervention to which they are randomly assigned, within the predefined window, have at least 1 valid and determinate immunogenicity result after Dose 2, have blood collection within an appropriate window after Dose 2, and have no other important protocol deviations.
Dose 1 all-available immunogenicity	All randomized participants who receive at least 1 dose of the study intervention with at least 1 valid and determinate immunogenicity result after Dose 2.
Evaluable efficacy	All eligible randomized participants who receive all study intervention dose(s) as randomized within the predefined window and have no other important protocol deviations.
All-available efficacy	All randomized participants who receive at least 1 dose of the study intervention.
Safety	All randomized participants who receive at least 1 dose of the study drug.

8.2. **Populations for Analyses**

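### The interim at 18 cases is half of a count that includes a second dose level Part 2 does not have, and Section 8.1.2 keeps the final level at 0.05 after a 0.003 efficacy look

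*Combined protocol and SAP*

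**What the plan says.** **Where 18 comes from.** The footnote in Section 8.4 takes a null VE of 30%, an alternative of 80% and an attack rate of 0.05 in the unvaccinated. It obtains p0 = 0.41 and p1 = 0.17, "which gives a total target number of events of around 31", split into about 5 vaccine and 26 placebo cases. It continues "so if we add in the other dose then looking at around 36 total events" and concludes "So interim analysis at 1/2 * 36 = 18 events (or 6 months post last vaccination, whichever is first".

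**The Part 2 design.** Section 4.2.1: "eligible participants will be randomized in a 1:1 ratio to either active (VXA-CoV2-1.1-S) or control (matching placebo tablets) group". The active arm gets one dose level, chosen after Part 1. Section 8.1.2: "The total sample size for Part 2 of this study (2 arms) would be 682"; 800 are randomized, 400 per arm.

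**The levels.** Section 8.1.2: "All testing will be performed at alpha = 0.05. All tests will be two-sided". It cites O'Brien-Fleming boundaries and allows a stop for efficacy at 0.003. It then says "If the decision is made to continue the study until completion at 6 months post last vaccination, alpha" is to be at most 0.05. Section 8.4 gives 0.003 as the level at which, "at the interim analysis, the study may be stopped for overwhelming efficacy", and counts a study that completes as planned as successful at P of 0.05 or less.

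**Timing.** Under Section 4.2.2 the final efficacy analysis follows the last participant's Month 7 visit. No section ends Part 2 at a number of cases.

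**The trigger event.** Section 8.4 says the look will happen at 18 confirmed SARS-CoV-2 infections. Sections 1.1, 4.2.2 and 8.1.2 make it optional, at 18 cases of confirmed COVID-19. The primary endpoint in Section 8.3.2 names both confirmed illness and serologically confirmed infection, but its VE ratio counts illness only.

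**The concern.** The derivation of 18 does not describe this trial: it counts cases in an arm that Part 2 lacks. A reader who takes 18 as the halfway point would misjudge the information at the look.

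The decision levels are a separate matter. A look that can end the trial for efficacy uses some of the type I error. If 0.003 is spent there and the full 0.05 is applied at the end, the overall level exceeds the two-sided 0.05 that the plan sets for itself. The final P-value threshold would then be open to challenge.

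The two trigger definitions could also start the look at different times, because infections and illnesses are different counts.

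**Working it through.** **1. Reproduce the footnote.** At 1:1 allocation the vaccine share of cases is (1 − VE)/(2 − VE).

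- p0 = 0.7/1.7 = 0.412 and p1 = 0.2/1.2 = 0.167, as printed.
- An exact binomial test at one-sided 0.025 first reaches 85% power at 31 cases (success at 7 or fewer vaccine cases; error 0.0245, power 86.8%). The plan does not state the power behind 31; 85% is inferred because it reproduces the figure.
- Split: 31 × 0.167 = 5.2 vaccine and 25.8 placebo. A second active arm adds 5.2, giving 36.2. So 36 is a three-arm count.
- For the two arms of Part 2, half of 31 is 15.5, and 18/31 = 58%.

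**2. Cases the trial would end with.** Expected total = n per arm × 0.05 × (2 − VE), with the plan's 5% attack rate.

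| n per arm | VE | Expected cases | 18 as a share |
|---|---|---|---|
| 341 | 90% | 18.8 | 96% |
| 400 | 80% | 24 | 75% |
| 400 | 30% | 34 | 53% |
| 400 | 0 | 40 | 45% |

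The information fraction at 18 cases is therefore unknown until the end.

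**3. Where 0.003 comes from.** An O'Brien-Fleming-type spending function at fraction t spends 4 × [1 − Φ(z/√t)], with z = 2.241 (the 0.9875 quantile). At t = 0.5 this is 4 × [1 − Φ(3.170)] = 0.00305, and the matching final level is 0.0490. The printed 0.003 fits 18/36, but its partner is 0.049, not 0.05.

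**4. Overall alpha of 0.003 then 0.05.** With t = 18/final cases, the two statistics are bivariate normal with correlation √t. Overall alpha = 1 − P(|Z1| < 2.968 and |Z2| < 1.960). The efficacy-only column lets the look stop for efficacy alone: half the two-sided figure plus 0.025. The last column is the final level that brings the two-sided figure back to 0.05 after a 0.003 look.

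| Final cases | t | Two-sided look | Efficacy-only look | Final level needed |
|---|---|---|---|---|
| 31 | 0.581 | 0.0507 | 0.0503 | 0.0493 |
| 36 | 0.500 | 0.0510 | 0.0505 | 0.0490 |
| 40 | 0.450 | 0.0512 | 0.0506 | 0.0488 |

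At 60 cases the final level needed is 0.0482. At the 18.8 to 24 cases expected if VE is 80% to 90%, overall alpha is at most 0.0502.

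**5. Exact check.** Take the vaccine cases as binomial given the total, double the one-sided P, look at 18 cases at 0.003, then test at 0.05, for every final total from 19 to 60.

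- Against VE 30% (p0 = 0.412), efficacy-side error passes 0.025 only at 34, 43 and 46 cases: 0.0253, 0.0254 and 0.0251.
- At 34 cases, 2 × P(X ≤ 8) = 0.0499. Eight vaccine cases succeed at 0.05 but not at 0.0491, the level for 18/34, so the rule moves to 7 or fewer.
- The two-sided exact total never exceeds 0.0481.
- Against VE = 0 (p = 0.5), efficacy-side error stays below 0.025 at every total.

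**The case against.** The best defence is that nothing of substance turns on this. The look is optional in three of the four places that describe it. Section 8.4 names O'Brien-Fleming methods and leaves detail to the SAP. Its 0.05 bullet follows the sentence on what happens if 18 cases are not reached, so it can be read as the no-look case, for which 0.05 is correct. The exact test is conservative at nearly every total. Section 8.3.2 names a beta-binomial model without a prior, so the actual test may behave differently.

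Most of this stands as to size. It does not remove the fault: Section 8.1.2 applies 0.05 expressly to a study that continues past the look, and a promise of further detail does not withdraw a printed level.

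Four stronger readings are tempting, and the documents do not support them.

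- *Overall alpha is 0.003 + 0.05 = 0.053.* That ignores the correlation between the two analyses; step 4 gives at most 0.0512 at 40 cases.
- *18 is the wrong number, or 31 is the right target.* 18 does no harm as a trigger. Part 2 does not run to a case count, and under its own attack rate and VE of 80% to 90% it would not be expected to reach 31.
- *Printing 0.049 as the final level cures it.* It gives 0.0502 at 40 cases. Even 0.0488 gives 0.0506 at 60, and a calendar-timed analysis puts no cap on cases.
- *The other dose means the Week 4 administration.* The footnote sets it against a calculation for one primary dose versus placebo, and the 5 cases added equal one vaccine arm's share.

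**Conclusion.** Wrong as written, and minor. The 36 behind the interim belongs to a design with two active dose levels; 18 is 58% of the footnote's one-dose figure, and neither 31 nor 36 is the trial's final count. Section 8.1.2 leaves the final level unadjusted after an efficacy look. The nominal excess is 0.0003 to 0.0012 at 31 to 40 final cases, depending on the total and on whether only the efficacy side can stop. Exactly, against VE 30%, efficacy-side error exceeds 0.025 at 3 of the 42 totals examined, by at most 0.0004.

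These figures treat 0.003 and 0.05 as P-value levels, as Sections 8.1.2 and 8.4 print them, and assume a 5% attack rate where expected counts are used. The beta-binomial analysis cannot be computed without its prior. The two trigger events are an inconsistency of wording, with no number attached.

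**What to change.** - In the 8.4 footnote, delete the second-dose step and state 18 cases as a fixed trigger, without giving 31 as a target.
- Keep 0.003 at the look. If the look is taken, compute the final level from 18 divided by the observed final number of cases so that overall two-sided alpha is 0.05: about 0.0493 at 31, 0.0490 at 36, 0.0488 at 40 and 0.0482 at 60. If no look is taken, keep 0.05. Say this in both 8.1.2 and 8.4.
- In 1.1, 4.2.2, 8.1.2 and 8.4, use one trigger event, the confirmed COVID-19 illness counted in the primary VE ratio, and say consistently whether the look is planned or optional.

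Sample size and visits do not change. The cost is a slightly stricter final level when the look is taken. In the exact test against VE 30%, the success rule changes only at 34, 43 and 46 of the totals from 19 to 60, but power falls there: at VE 80%, from 90% to 81% at 34 cases and from 96% to 91% at 43. If the null is VE = 0, the rule changes only at 44 cases (2 × P(X ≤ 15) = 0.04877 against a level of 0.04866) and 51 cases (2 × P(X ≤ 18) = 0.04887 against 0.04844).

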8.5. Safety Oversight

8.5.1. Internal Sponsor Review

Safety data will be monitored on an ongoing basis by the Investigator (or medically qualified designee) and the Sponsor's Medical Monitor (or designee) in order to promptly identify and flag any event that potentially contributes to a halting rule (Section 6.1).

A Sponsor's Medical Monitor (or designee) will perform the oversight of safety for this study. Additional local medical monitors may also be employed to aid with safety oversight locally. The lead Medical Monitor will be a physician experienced in the conduct of research clinical studies whose primary responsibility will be to monitor participant safety. The Medical Monitor will be responsible for reviewing the cumulative safety data, including a review of safety laboratory test results and adverse event reporting. The Medical Monitor will be familiar with study-specific data as well as relevant background information about the disease, investigational drug, and target population under study. The Medical Monitor(s) will be empowered to request an IDMC safety review which can suspend the study, recommend amendments to the protocol, and/or to request further information.

